2.4 Secondary Objectives

1. To compare the effect of the addition of elotuzumab versus placebo to prednisone on complete remission at 48 weeks.
2. To compare the effect of the addition of elotuzumab versus placebo to prednisone on the number of disease flares (as defined in Section 3.5.3) per participant over time.
3. To compare the effect of the addition of elotuzumab versus placebo to prednisone on the change from baseline in Physician Global Assessment (PhGA) at 4, 8, 12, 16, 20, 24, 28, 32, 36, 40, 44, and 48 weeks.
4. To compare the effect of the addition of elotuzumab versus placebo to prednisone on Patient Global Assessment (PGA) at 4, 8, 12, 16, 20, 24, 28, 32, 36, 40, 44, and 48 weeks.
5. To compare the effect of the addition of elotuzumab versus placebo to prednisone on safety.

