3.5.4 Physician and Patient Global Assessment Visual Analog Scale (VAS)

The PhGA of the participant's current disease activity is recorded on a 100 mm linear horizontal VAS, where the left hand extreme of the line is considered "Very Good" (symptom free and no IgG4-RD symptoms) and the right hand extreme is considered "Very Bad" (maximum IgG4-RD activity). Only active disease (as opposed to damage) is considered in the scoring of the PhGA. The PGA of current disease activity will be assessed on an identical VAS. During Part 1A, assessments will be performed at Screening, Baseline/Day 0, Weeks 1, 5, 9, 16, 24 and 48, as well as at any interim visit conducted because of the possibility of recurrent disease or for the purpose of assessing a potential AE. During Part 1B and 2, assessments will be performed at Screening, Baseline/Day 0, Weeks 4, 8, 12, 16, 20, 24, 28, 32, 36, 40, 44, and 48, as well as at any interim visit conducted because of the possibility of recurrent disease or for the purpose of assessing a potential AE. A sample assessment form is included in **Appendix 4: PhGA and PGA VAS**.

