3.7 Stratification, Randomization, and Blinding/Masking

In Part 2, after participants sign the consent form, those eligible will be randomized in a 2:1 ratio to receive elotuzumab versus placebo. Randomization will be stratified by whether participants have newly-diagnosed or relapsing disease at entry.

Randomization will be accomplished through a password-protected, web-based, randomization system. The investigators, clinic personnel, and participants will not be informed regarding the intervention assignment until the study is unblinded. Laboratories performing assays for this protocol will be masked to the identity and group assignment of biological materials to be studied.

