13.4.3 Supportive Analyses of the Primary Endpoint

A supportive analysis of the primary endpoint will consider participants who drop out of the study prior to reaching week 48 without evidence of disease flare, initiation of non-protocol therapy, or other indications of increased disease activity as missing-completely-at-random (MCAR). Descriptive statistics and the Wilcoxon-Mann-Whitney test will be repeated in the subgroup of the mITT population excluding participants with data MCAR. A masked data review panel will evaluate participant disposition and all disease activity assessments in a blinded manner to define the types of missing data. In addition, analysis of the primary endpoint will be repeated as a van Elteren test with a covariate for the stratification factor of newly-diagnosed versus relapsing disease at study entry. As an additional supportive analysis which does not assume data are MCAR, a two-dimensional tipping point analysis of missing data will be conducted. Additional details on supportive analysis will be specified in the Statistical Analysis Plan.

Supportive analyses of the primary endpoint will be repeated in the PP populations and as a preplanned subgroup analysis in participants who are identified as having elevated serum IgG4 level prior to initiation of study therapy. The subgroup is defined as any serum IgG4 concentration greater than 1.5 times the upper limit of normal that is obtained within 6 months of the Baseline visit or at the baseline assessment of Serum IgG subclasses.

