13.4.4 Analyses of Secondary and Other Endpoints

The key secondary endpoint for Part 2 is complete response at 48 weeks, defined as an IgG4-RD RI Score of 0 and a glucocorticoid dose of 0 mg/day and no flare since beginning treatment. A fixed sequence testing procedure will be conducted with the primary efficacy endpoint, to control the overall Type I error rate at 0.05. Specifically, if the between-group comparison of disease response at 48 weeks reaches statistical significance, a comparison of the rates of complete remission at 48 weeks will be performed using a Fisher's Exact test with a two-sided Type I α of 0.05. If the between-group comparison of disease response at 48 weeks fails to reach statistical significance,

inferences on complete remission will be supportive without overall Type I error control. The proportion in complete remission in each arm will be reported with two-sided 95% Clopper-Pearson confidence intervals. All participants in the mITT population who drop out of the study prior to reaching week 48 for any reason, including a disease flare, initiation of non-protocol therapy, or any other reason to cause them to be unevaluable using the IgG4 Responder Index, will be defined as not achieving complete remission.

All inferential analyses for the additional secondary efficacy endpoints are considered supportive; p-values for test of differences among groups will be presented without adjustment for multiple comparisons. All secondary endpoints will be analyzed in the mITT and PP populations, and in the subgroup with elevated serum IgG4 level prior to initiation of study therapy.

For all dichotomous efficacy endpoints, Fisher's Exact tests will be conducted and two-sided 95% Clopper-Pearson confidence intervals will be reported.

Frequency counts of the number of disease flares and the number of organ sites with disease-related damage will be reported by arm, and between-group comparison will be performed using Fisher's Exact Test.

For secondary continuous efficacy endpoints, including the Physician Global Assessment and Patient Global Assessment, descriptive statistics will be used to summarize the distribution of scores in each arm. The absolute change from baseline will be analyzed using an analysis of covariance model (ANCOVA) with treatment allocation as the independent variable.

Treatment group differences for the safety endpoints will be compared using a Fisher's exact test.

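### The PhGA and PGA change analysis is called an ANCOVA but names treatment as its only term: baseline VAS and the randomisation stratum should be stated as covariates (minor; supportive analyses only)

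*Combined protocol and SAP*

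**What the plan says.** Section 13.4.4 introduces the model with "For secondary continuous efficacy endpoints, including the Physician Global Assessment and Patient Global Assessment" and then states: "The absolute change from baseline will be analyzed using an analysis of covariance model (ANCOVA) with treatment allocation as the independent variable". Treatment is the only term given.

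Four other places bear on it:

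- **Baseline is measured.** Section 3.5.4: "During Part 1B and 2, assessments will be performed at Screening, Baseline/Day 0, Weeks 4, 8, 12, 16", and then every four weeks to Week 48.
- **There are many time points.** Section 2.4, objective 3, concerns "the change from baseline in Physician Global Assessment (PhGA) at 4, 8, 12, 16" and so on to Week 48, twelve post-baseline visits in all. Objective 4 lists the same visits for the PGA.
- **The design has a stratum.** Section 3.7: "Randomization will be stratified by whether participants have newly-diagnosed or relapsing disease at entry". Section 13.3 repeats this.
- **The stratum enters one analysis only.** Section 13.4.3 repeats the primary analysis as "a van Elteren test with a covariate for the stratification factor of newly-diagnosed versus relapsing disease at study entry".

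On status, section 13.4.4 says: "All inferential analyses for the additional secondary efficacy endpoints are considered supportive". P-values are to be shown without multiplicity adjustment.

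**The concern.** An ANCOVA has a covariate by definition, and this one names none. The sentence can be carried out in two ways, with different consequences that do not add up.

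- **Run literally**, it is a two-sample comparison of change scores. Baseline enters only by subtraction, which fixes its coefficient at 1 instead of estimating it. In most plausible settings that gives a larger standard error than adjustment would.
- **Run with a covariate because of the label**, the choice of covariate is not fixed in this document. It could be baseline, stratum or both. This consequence is not quantified here.

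The stratum is a separate matter. If the stratified factor predicts outcome and the model omits it, the model-based standard error is too large and the test is conservative.

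At stake is the precision and unambiguous specification of two secondary endpoints at up to 12 visits each, that is 2 x 12 = 24 contrasts in the mITT population if every visit is analysed.

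**Working it through.** **The plan's own figures.** None is given for PhGA or PGA: no SD, correlation, effect size or power. The Part 2 figures in section 13.7 reproduce and are not in dispute:

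- Noether: N = (1.960 + 1.282)^2 / (12 x 2/3 x 1/3 x 0.25^2) = 63.04, against 63 stated. Power at 63 is 0.8998, against 90% stated.
- Fisher exact power, 65% versus 25% with 42 and 21 participants: 0.8261, against 0.826 stated.

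**Inputs.** From the document: N = 63, 2:1, stratified by disease status. Assumed: baseline SD 1; follow-up SD k = 0.75, 1 or 1.25; baseline-to-follow-up correlation rho from 0.2 to 0.8; all 63 participants observed at the visit.

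**Step 1: variance per observation.**

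- Treatment only, on change: k^2 + 1 - 2 x rho x k
- With baseline as covariate: k^2 x (1 - rho^2)

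**Step 2: cost of the extra terms.** Chance imbalance in baseline inflates the variance by about 60/59, or 1.7%. Stratified randomisation keeps the stratum nearly balanced between arms, so its cost is negligible apart from one degree of freedom. The critical values are t(59) = 2.0010 and t(61) = 1.9996, a ratio of 1.0007.

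**Step 3: CI width ratio** = sqrt(variance ratio x 60/59) x 1.0007.

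Example, k = 1, rho = 0.5: variance ratio 0.75 / 1.00 = 0.75; x 60/59 = 0.763; square root 0.873; x 1.0007 = 0.874, so 12.6% narrower.

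Example, k = 1.25, rho = 0.8: 0.5625 / 0.5625 = 1; x 60/59 = 1.017; square root 1.0084; x 1.0007 = 1.009, so 0.9% wider.

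Change in 95% CI width (nearly the same as the change in SE) from adding baseline and stratum, when the stratum has no effect:

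| Follow-up SD / baseline SD | rho 0.2 | 0.3 | 0.5 | 0.7 | 0.8 |
|---|---|---|---|---|---|
| 0.75 | -34% | -32% | -27% | -25% | -25% |
| 1.00 | -22% | -19% | -13% | -7% | -4% |
| 1.25 | -14% | -11% | -5% | -0.1% | +0.9% |

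One of the 15 cells loses, and one is break-even. Simulation (8,000 trials per cell, permuted blocks of 3 within stratum) agrees: the CI ratio is 0.999 at k = 1.25, rho 0.7; 1.009 at k = 1.25, rho 0.8; and 0.957 at k = 1, rho 0.8.

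**Step 4: the stratum.** Simulation of 20,000 trials per cell, with k = 1, rho 0.5, strata 50:50 and blocks of 3. The document gives no block size; blocks of 6 give CI-width reductions within 0.1 point. Each entry gives treatment only / plus baseline / plus baseline and stratum.

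| Stratum effect | Mean CI width | Type I error | Empirical SE (two adjusted models) |
|---|---|---|---|
| 0 | 1.065 / 0.930 / 0.931 | 0.049 / 0.049 / 0.049 | 0.232 / 0.232 |
| 0.5 SD | 1.098 / 0.968 / 0.930 | 0.046 / 0.042 / 0.051 | 0.235 / 0.234 |
| 1 SD | 1.193 / 1.077 / 0.931 | 0.030 / 0.025 / 0.050 | 0.237 / 0.235 |

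Adding the stratum to the baseline-adjusted model changes the CI width by 0.931/0.930 - 1 = +0.1%, 0.930/0.968 - 1 = -4% and 0.931/1.077 - 1 = -14%. With strata 30:70, the last two become -3.3% and -11.8%. The empirical SE barely moves, so the stratum term corrects the reported standard error and adds almost no real precision.

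**The case against.** **The label already implies a covariate.** A statistician who reads ANCOVA may treat the sentence as incomplete wording and put baseline in. This is fair. The baseline gains in the working then do not arise, and what remains is that the model terms are not written down.

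**The terms may be in a document not supplied.** Section 13.4.3 says "Additional details on supportive analysis will be specified in the Statistical Analysis Plan", and section 13.5.2 defers the content of safety reports in the same way. Neither sentence covers this model. Still, a reader might infer that the terms were never pre-specified, and silence here does not establish that.

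**Leaving out the stratum matches the primary analysis**, which is itself unstratified, with the stratified test as support. This stands as a matter of consistency. The document does not show that the stratum is prognostic, and if it is, the omission errs on the conservative side.

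**The size is not fixed by the document.** Correct: a spread from 34% narrower to 0.9% wider reflects assumptions about SD and correlation. The plan also promises no confidence intervals for the continuous endpoints, so CI width here stands in for the standard error behind the p-values.

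**A reader might infer bias, or harm to the main result.** Neither follows. Under randomisation, the treatment-only comparison of change is unbiased. These endpoints also sit outside the fixed testing sequence.

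**Conclusion.** The point holds as a minor one. Section 13.4.4 calls for an ANCOVA with treatment as its only named term, and nothing else in the document supplies baseline VAS or the randomisation stratum for this model. That a baseline covariate was meant is an inference from the label, which the document neither confirms nor excludes.

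If the sentence is run literally, the loss is usually material with equal or smaller follow-up SD. With larger follow-up SD and high correlation it shrinks to nothing or reverses slightly. A prognostic stratum of 0.5 to 1 SD would leave the baseline-adjusted test at about 0.042 to 0.025 instead of 0.05. If the stratum is not prognostic, including it costs about 0.1% in CI width. All of this rests on assumed SDs, correlations and stratum effects, and on complete data at the visit.

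Only supportive analyses are touched. The Wilcoxon-Mann-Whitney test, the complete-remission comparison, N = 63 and the trial's type I error control are unaffected.

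**What to change.** State in section 13.4.4, or in the Statistical Analysis Plan before unblinding, that change in PhGA and PGA at each visit will be analysed by ANCOVA with three terms: treatment, the baseline value of the same VAS, and newly-diagnosed versus relapsing disease. If a separate SAP already names the terms, align the two texts.

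The cost is one sentence. Both covariates are already collected, so no data, visits or participants are added. The two extra degrees of freedom cost at most about 2% in variance at N = 63.

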3.2 Primary Endpoints

Part 1: Primary Safety Endpoint

The proportion of participants in each cohort who experience at least one Grade 3 or higher adverse event during study participation.

Part 2: Primary Efficacy Endpoint

Disease response at 48 weeks, defined as percent improvement in the IgG4-RD RI score over baseline.

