3.3 Secondary Endpoints

Part 2: Key Secondary Efficacy Endpoint

1. Complete remission at 48 weeks, defined as an IgG4-RD RI Score of 0 and a glucocorticoid dose of 0 mg/day and no flare since beginning treatment.

Part 1 and Part 2: Additional Secondary Efficacy Endpoints

1. The proportion of participants that reach the following threshold levels of IgG4-RD RI improvement at 48 weeks: 50% and 75%.
2. Number of disease flares, as defined in Section 3.5.3.
3. Change in PhGA from baseline.
4. Change in PGA from baseline.
5. Disease-related damage, as measured by the damage section of the IgG4-RD RI.

Part 1 and Part 2: Secondary Safety Endpoints

1. The proportion of participants who experience at least one Grade 2 or higher adverse event.
2. The proportion of participants with a Grade 3 or higher infection.
3. The proportion of participants who experience a malignancy.
4. The proportion of participants who experience a Hepatotoxicity, defined as increase in the aspartate aminotransferase (AST) or alanine aminotransferase (ALT) to elevations three times the upper limit of normal.
5. The proportion of participants who experience a serious adverse event.
6. The proportion of participants who experience infusion reactions, defined as any adverse reaction within 24 hours of infusion which are Grade 2 or higher events and at least possibly related to study drug.

Part 2: Secondary Safety Endpoint

1. The proportion of participants who experience at least one Grade 3 or higher adverse event.

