6.6 Premature Discontinuation of Investigational Agent

Study treatment will be discontinued for any participant who experiences any of the following:

- Pregnancy
- Any Grade 4 or higher infection
- For AEs associated with laboratory evaluations, any of the following lab abnormalities that persist longer than 5 days:
 - i. eGFR < 30 ml/minute/1.73m²
 - ii. WBC ≤ 1.5 x 10⁹/L
 - iii. Platelet count < 50 x 10⁹/L
 - iv. Hemoglobin < 8 g/dL
 - v. ANC < 1.0 x 10⁹/L
 - vi. ALT or AST elevation > 5 times ULN
 - vii. Total bilirubin > 3 times ULN. If Gilbert's disease, total bilirubin > 3 times baseline value.
- For AEs associated with clinical evaluations, any Grade 3 or higher event as defined by the National Cancer Institute-Common Terminology Criteria for Adverse Events (NCI-CTCAE) that is possibly, or definitely related to elotuzumab including anaphylaxis (see **Appendix 7: Clinical Criteria for Diagnosing Anaphylaxis**)[39] or infusion reaction
- Malignancy excluding squamous cell and basal cell carcinoma of the skin
- Disease flare, as defined in Section 3.5.3
- Participants who decide to discontinue the treatment
- The investigator believes that the study treatment is no longer in the best interest of the participant.

Participants will be expected to remain in the study for follow up despite discontinuation of study drug. Participants who discontinue protocol-specified treatment requirements will be treated as medically indicated according to physician discretion.

7 Concomitant Medications

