12.4 Collecting and Recording of Adverse Events

12.4.1 Collection Period

All adverse events, regardless of severity, should be recorded in the study source documentation and will be captured in the database per the following criteria:

- Adverse events of all grades will be collected from the time the participant signs the informed consent until he/she initiates study intervention or until he/she is determined to be ineligible to receive study intervention, if the investigator determines that the adverse event is related to a study-mandated procedure, treatment, or change in concurrent medication.
- Adverse events of all grades will be collected from the initiation of study intervention until completion of the study or until 30 days after the participant is prematurely withdrawn (without withdrawal of consent) or withdraws from the study, whichever occurs first.

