13.4 Analysis Plan

13.4.1 Analysis Populations

In Part 1:

Safety population: will be defined for each treatment regimen as all participants who received any amount of investigational product.

In Part 2:

Modified Intent-to-Treat (mITT) population: will be defined as all participants who undergo random assignment and receive any amount of elotuzumab / elotuzumab-placebo. The primary efficacy analyses will be based on the mITT population according to the groups to which the participants are assigned.

Per Protocol (PP) population: will be defined as the subgroup of participants in the mITT population who (1) receive at least 5 of 6 elotuzumab / elotuzumab-placebo infusions or discontinue treatment due to a disease flare (2) receive at least 80% and no more than 120% of the cumulative dose of prednisone during the 10 week taper defined in Section 7.1.1.3, (3) adhere to the permitted single course of glucocorticoids for non-IgG4-RD indications defined in Section 7.2 and (4) have no major protocol deviations or ineligible entry criteria that would impact efficacy assessments through week 48.

A masked data review will evaluate deviations from the protocol in a blinded manner for impact on the efficacy assessments and exclusion from the PP population. This may include, but is not limited to, violations of entry criteria, departures from assigned treatment regimen, modifications of concurrent therapy, failure to complete study visits, or administration of study procedures outside the specified visit windows.

Safety population: will be defined as all participants who received any amount of at least one elotuzumab / elotuzumab-placebo infusion. Safety analyses will be based on the actual treatment which the participants receive.

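### Part 2 safety proportions count events under post-flare rescue therapy in the study-treatment group, with no on-regimen analysis beside them, so an elotuzumab excess can be diluted

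*Combined protocol and SAP*

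**What the plan says.** Section 3.3 defines the Part 2 safety endpoints as participant-level proportions, for example "The proportion of participants who experience at least one Grade 3 or higher adverse event". Only the infusion-reaction endpoint has a time limit: "defined as any adverse reaction within 24 hours of infusion which are Grade 2 or higher events". Section 13.4.1 restricts the Part 2 safety population to dosed participants ("will be defined as all participants who received any amount of at least one elotuzumab / elotuzumab-placebo infusion") and groups them by what they received: "Safety analyses will be based on the actual treatment which the participants receive". The planned comparison, in Section 13.4.4, is "Treatment group differences for the safety endpoints will be compared using a Fisher's exact test".

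Section 6.6 lists a disease flare among the reasons to discontinue study treatment, keeps the participant in follow-up, and adds: "Participants who discontinue protocol-specified treatment requirements will be treated as medically indicated according to physician discretion". Section 7.3 lifts the ban on other immunosuppressants when they are given for a flare. Section 11.1 continues Part 2 follow-up to Week 48 whether or not study medication has stopped. Under Section 12.4.1, adverse events of all grades are collected from first dose to study completion, or to 30 days after early withdrawal.

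Section 12.3.1 defines treatment-emergent for abnormal clinical and laboratory evaluations, but no endpoint or Part 2 analysis uses the term.

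**The concern.** Comparing safety between arms is a secondary objective (Section 2.4), and Section 13.7 gives safety as one reason for the 2:1 allocation. A participant who flares on placebo and then takes glucocorticoids or another immunosuppressant still counts as a placebo participant for every later infection or Grade 3 event. Grouping by actual treatment does not change this, because the infusions received were placebo.

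If elotuzumab prevents flares, rescue is concentrated in the placebo group. The protocol itself reports more infections with elotuzumab than with controls (Section 5.1.3) and lists infection as a corticosteroid risk (Section 5.2.1). Rescue-period events would then raise the placebo proportion and narrow a real elotuzumab excess, which is the unfavourable direction for a safety comparison.

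Relatedness coding will not separate the sources cleanly. Section 12.3.2 has events whose cause may overlap between study product and glucocorticoids recorded as related or possibly related to elotuzumab. For efficacy, Section 13.4.2 deals with flare and rescue explicitly, by assigning 0% response. For safety the plan is silent.

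**Working it through.** **The plan's own figures.** Section 13.7 gives no safety rates or safety power, but it does give an exact Fisher power for the same arm sizes (42 v 21). Full enumeration of both binomials at 65% v 25%, two-sided 0.05, gives 0.826, as stated. The same routine is used below.

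**Illustration 1: a moderate harm.** Assumptions, none of them planned rates:
- Flares are uniform over Weeks 10 to 48.
- Flare rates (elotuzumab v placebo) are 12% v 39%, or 25% v 60%. The 39% is relapse on continued prednisone alone and the 12% is failure on cyclophosphamide plus prednisone, both from trials cited in Section 1.1.2; they are proxies. The second pair has no source in the documents.
- The event hazard per 48 weeks on regimen is 0.10 on placebo and 0.20 on elotuzumab.
- After rescue the hazard is k times 0.10 in either group.

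Share of follow-up off regimen = flare rate × (38/48)/2:
- Placebo: 0.39 × 0.396 = 15%; 0.60 × 0.396 = 24%.
- Elotuzumab: 0.12 × 0.396 = 5%; 0.25 × 0.396 = 10%.

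Without rescue, the risks are 1 − exp(−0.20) = 0.1813 and 1 − exp(−0.10) = 0.0952, ratio 1.90.

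With rescue, for flare rate f, on-regimen hazard h, rescue hazard r, d = r − h and L = 38/48:

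risk = (1 − f)(1 − e^(−h)) + f[1 − e^(−h)(1 − e^(−dL))/(dL)]

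Worked case, placebo, f = 0.39, k = 2: d = 0.10 and (1 − e^(−0.0792))/0.0792 = 0.9614. Risk = 0.61 × 0.0952 + 0.39 × (1 − 0.9048 × 0.9614) = 0.1088. On elotuzumab the rescue hazard then equals its own 0.20, so its risk stays at 0.1813 and the ratio is 1.67.

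| Flare (elotuzumab v placebo) | k | Risk, elotuzumab | Risk, placebo | Ratio | Extra placebo participants of 21 | Fisher power |
|---|---|---|---|---|---|---|
| no rescue | – | 0.181 | 0.095 | 1.90 | – | 0.098 |
| 12% v 39% | 2 | 0.181 | 0.109 | 1.67 | 0.29 | 0.077 |
| 25% v 60% | 2 | 0.181 | 0.116 | 1.56 | 0.44 | 0.068 |
| 12% v 39% | 3 | 0.185 | 0.122 | 1.52 | 0.56 | 0.066 |
| 25% v 60% | 3 | 0.189 | 0.136 | 1.39 | 0.86 | 0.056 |

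If rescue carries only the placebo hazard (k = 1), the ratios are 1.86 and 1.82.

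**Illustration 2: a harm large enough to detect.** Assume on-treatment Grade 3+ risks of 40% v 10% (power 0.705) and flare rates of 12% v 39%. Risk = 1 − (1 − on-treatment risk)(1 − flare rate × rescue-period risk). With a rescue-period risk of 20%:
- Elotuzumab: 1 − 0.60 × (1 − 0.024) = 0.414.
- Placebo: 1 − 0.90 × (1 − 0.078) = 0.170.
- The difference falls from 30 to 24.4 points and power to 0.458.

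Rescue-period risks of 10% and 40% give 27.2 points (power 0.577) and 18.8 points (power 0.264). With flare equal at 39% in both groups and a 20% rescue-period risk, the difference is 27.7 points (power 0.559), so part of the loss needs no flare imbalance.

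**Pre-dose events.** Adding an assumed 5% pre-dose risk to both groups in the 12% v 39%, 20% case moves the difference from 24.4 to 23.2 points and power from 0.458 to 0.395. This is dilution common to both groups.

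**The case against.** Counting everything to Week 48 in randomised, dosed participants is a legitimate treatment-policy comparison. It answers what happens when elotuzumab is added to prednisone, rescue included. An on-regimen window conditions on a post-randomisation event, shortens follow-up informatively, and suits delayed outcomes such as malignancy poorly. That stands. It is why the on-regimen analysis should be supportive and not a replacement.

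The absolute shift in the first illustration is below one placebo participant, and the test would miss that harm about nine times in ten without any rescue. That also stands: sample size is the main limit on detecting a moderate excess. Illustration 2 shows that the loss is material only for a large harm.

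Other provisions help in part: attribution to elotuzumab and prednisone (Section 12.3.2), safety-signal review by arm (Section 12.11.1) and tabulated medication use (Section 13.4.5). None sets a window for the final comparison.

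A reader might infer three stronger claims that the text does not support:
- **That every event from consent counts.** Section 12.4.1 opens with "Adverse events of all grades will be collected from the time the participant signs the informed consent until he/she initiates study intervention", but limits that period to events related to a study-mandated procedure, treatment or change in concurrent medication. Appendix 1 places randomisation at Baseline/Day 0, so such events should be similar in both groups.
- **That events are charged to the assigned arm over all randomised participants.** Section 13.4.1 uses dosed participants by actual treatment. Section 13.4.4 blurs this by sending all secondary endpoints to the mITT and PP populations.
- **That the plan fixes whole-participation counting for Part 2 by the phrase** "who experience at least one Grade 3 or higher adverse event during study participation". That is the Part 1 endpoint, for uncontrolled cohorts summarised descriptively.

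**Conclusion.** The point holds as a gap in the safety analysis. Apart from infusion reactions, events after a flare, off study drug and under rescue, count in the group of the study infusions, and no planned analysis separates them. If placebo participants flare more, and rescue carries appreciable risk, an elotuzumab excess is diluted.

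The direction follows from the text and those two conditions. The size does not, because the documents give no safety rates, no Part 2 flare rates and no rescue hazards. On the assumptions shown, a true ratio of 1.90 appears as 1.39 to 1.67, or 0.29 to 0.86 extra placebo participants of 21, with Fisher power of 0.056 to 0.077 against 0.098 without rescue. It would go too far to say that the plan will conceal harm, or that the Week 48 comparison is invalid. Pre-dose events are a minor, non-directional issue. The change is worth making because it is cheap and makes the safety result easier to interpret.

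**What to change.** In Section 13.4.4:

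1. Keep the Week 48 Fisher comparison as the treatment-policy analysis, restricted to events with onset or worsening after the start of the first infusion.
2. State that safety endpoints use the safety population by actual treatment, and reconcile this with the sentence placing all secondary endpoints in mITT and PP.
3. Add a supportive on-regimen analysis: events per person-time from first infusion to the earlier of 8 weeks (one dosing interval) after the last infusion and the start of non-protocol immunosuppression, with a rate ratio and exact 95% confidence interval. Person-time is needed because a cut-off proportion alone would favour the group that stops earlier. For a participant dosed at Week 40 and never rescued, the window ends at Week 48, so essentially no follow-up is lost.
4. Show events after the start of rescue separately by group, and keep malignancy on whole follow-up.

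The cost is wording and one extra set of tables. Infusions are documented on the case report form (Section 6.3) and flare-treatment start and stop dates are recorded (Appendix 5); adverse-event onset dates are assumed to be on the adverse-event form. The downside is that on-regimen time may be informatively shortened and the rate ratio will be imprecise with 42 and 21 participants, so both analyses should be reported side by side.
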